
Concept and Rationale: Besides allogeneic stem cell transplantation (allo-SCT), the DNA methyltransferase inhibitor (DNMTi) azacitidine (AZA) is the only treatment proven to prolong survival in patients with higher risk myelodysplastic syndrome (HR-MDS). Nonetheless, HR-MDS patients treated with AZA have a median survival advantage of 9.5 months (24.5 vs 15 months median OS)¹ and the objective response rate is only 50% with most patients eventually relapsing within 2 years¹. Failure of DNMTi therapy occurs in the majority of treated patients and carries a dismal prognosis with a median survival of less than 6 months ². To date, no drug or combination of drugs have improved survival of MDS patients in the post-DNMTi failure setting in randomized trials, and there is currently no standard of care for those patients. Therefore, improving outcomes of MDS patients after failure of DNMTi remains a top clinical and research priority ³.
 
Histone deacetylase inhibitors (HDACi) comprise a group of drugs that share the ability to inhibit the important epigenetic eraser enzymes HDACs. As single agents, several HDACi exhibited only modest clinical activities in MDS^{4,5}. Therefore, the interest to develop these agents further has focused on combination-based strategies, usually with DNMTi. To date, no HDACi-DNMTi combination has improved survival of MDS patients in randomized studies when used in the frontline or the post-DNMTi failure setting. These observations suggest that while HDACi therapy has modest activity in MDS, DNMTi might not be the best choice for combination-based regimen with HDACi. Exploration of alternative agents to combine with HDACi in the post-DNMTi failure setting might be a more rational approach.
 
Recent advances in tumor immunology have facilitated understanding the role of immune escape as important mechanism of cancer progression and treatment resistance. One important mechanism which cancers employ commonly to evade the immune system involve the exploitation of T-cell inhibitory pathways and molecules such as the programmed death-1 (PD-1) and cytotoxic T-lymphocyte associated antigen-4 (CTLA-4) ^{6,7}. Immune checkpoint blockade with antibodies directed against PD-1, its ligand (PD-L1), and CTLA-4 has emerged as promising approaches to reverse immune evasion, and have resulted in a significant and durable clinical activity in some patients with advanced solid malignancies especially metastatic melanoma, lung cancer, bladder cancer, and Hodgkin disease ⁸⁻¹¹. Compared to expanding clinical applications of immune checkpoint inhibitors in solid tumors, the mechanisms of immune evasion in hematologic malignancies including MDS have not been fully elucidated. Several studies suggest that interaction between PD-1 and PD-L1 may induce immune evasion in MDS¹² and moreover the upregulation of these molecules could be associated with resistance to DNMTi therapy in MDS¹³.
 
Furthermore, recent studies suggest that myeloid-derived suppressor cells (MDSCs), which are significantly increased in bone marrows of MDS patients (~35% vs <5% in non-MDS bone marrow), play an important role in ineffective hematopoiesis in MDS¹⁴. MDSCs also induce resistance to immune checkpoint blockade (anti-CTLA4 and anti-PD1) in colon cancer bearing mice¹⁵. Importantly, in this mouse model MDSCs were significantly decreased by the use of the epigenetic modulator entinostat (ENT), leading to rejection of tumors when combined with immune checkpoint blockade¹⁵.
 
Primary Objective(s): To identify the maximum tolerated total dose (MTD) of entinostat given in combination with pembrolizumab (MK-3475) in post-HMA failure setting for patients with MDS.
 
Secondary Objective(s): To obtain a preliminary estimate of efficacy of entinostat in combination with pembrolizumab (MK-3475).

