Assessment of response will occur after 4 combination cycles and similar to part 1, those who achieve an objective response or SD will continue to receive the therapy till progression. Patients who progress or respond and subsequently lose response will be withdrawn from study. BM biopsy/aspirate and PB samples will be done at baseline, after first cycle of ENT monotherapy, every 2 cycles of combined therapy, and at time of progression or study discontinuation. Formal safety assessment will be performed at end of DLT-observing period (i.e. 1 ENT monotherapy cycle and 2 cycles of combined therapy) for each patient) for each DL to assess for any unexpected autoimmune or other toxicity. The cycle duration will be 21 days, the maximum number of treatment cycles of entinostat will be 18 cycles and for pembrolizumab (MK-3475) the maximum number of cycles will be 17. Cycle 2 to cycle 18, will have concurrent administration.

The following early stopping rule for excess toxicity in the expansion cohort will be used: We will cease enrollment in the expansion phase at the dose determined from dose escalation part of the study if we observe two or more DLTs among the first six evaluable patients enrolled in the expansion cohort. An evaluable patient is any patient who received a study drug. If the true toxicity rate is 50% or greater at the MTD then this rule will stop the trial with probability at least .89. Similarly, if the true toxicity rate is 33% at the MTD then this stopping rule will end the trial with probability .65. In that event, a new expansion cohort will start at the dose level immediately below the dose level that was expanded. If the dose level being expanded is dose level -1, then the study will be terminated.

Study Schema

Study design

Dose Escalation Schedule		
Dose Level	Dose*	
	Entinostat	Pembrolizumab
Level -1(Backup dose level)	8mg po D1	200mg
Level 1 (starting dose level)	8mg po D1,8	200mg
Level 2	8mg po D1,8,15	200mg

Number of Patients: 6-27

Main Criteria for Inclusion/Exclusion:

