We will perform '3+3' classical dose escalation design to determine dose limiting toxicity (DLT). The first 3 patients will receive ENT at dose level 1 (DL1: 8mg on D1, 8 of 21-day cycles). pembrolizumab (MK-3475) will be added starting day 1 cycle 2 at the approved dose of 200mg intravenously [IV] over 30 minutes on D1 of 21-day cycles) for 4 cycles (cycle 2-5). A safety committee that includes the study chair, the principal investigator from any study site that has enrolled a patient on the specific DL, as well as two sub-investigators from Yale will review safety data after enrollment of every 3 patients during the dose escalation phase. The committee will have the discretion to decide to enroll 3 more patients in the specific dose level even if no DLT occurred in the first 3 treated patients in that dose level if there are toxicity/safety concerns that did not qualify as DLT (maximum of 6 evaluable patients to be enrolled at any dose level). The committee can also decide to enroll patients at a lower dose level after the first 3 or after the first 6 patients enrolled in any dose level even if no or one DLT occurred at that dose level if there are toxicity/safety concerns that did not qualify as DLT. The following regarding enrollment in different dose levels will be considered guidance for the safety committee but can be modified in accordance of above: If no patient of the 3 patients treated with combined therapy at DL1 develops DLT, then dose level 2 (DL2) will be tested. For instance, DL2 will be with ENT at 8mg on D1, 8 and 15 and pembrolizumab (MK-3475) at 200mg IV on D1 of 21-day cycles. If 1 patient out of the 3 patients has DLT at DL1, we will expand cohort to 3 more patients and if 1 patient of the 6 patients has DLT (i.e. only 0/3 or 1/6), we will test next dose (DL2). If no patient of the 3 patients treated with combined therapy at DL2 develop DLT, then DL2 will be used for part 2 (expansion cohort). If 1 patient out of the 3 patients has DLT at DL2, we will expand cohort to 3 more patients and if 1 patient of the 6 patients has DLT (i.e. only 0/3 or 1/6), dose level 2 (DL2) will be used for part 2 (expansion cohort). If 2 or more patients of the 6 patients have DLT, DL1 will be used for expansion cohort. The cycle duration will be 21 days, the maximum number of treatment cycles of entinostat will be 18 cycles and for pembrolizumab (MK-3475) the maximum number of cycles will be 17. Cycle 2 to cycle 18, will have concurrent administration. In all the phases of the study, entinostat will be administered in clinic within 2 hours before administration of pembrolizumab (MK-3475). Entinostat will be stored at the pharmacy and it will not be given for the patient to take home.

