5.6 Duration of Follow Up

Patients will be followed closely throughout the study period and for 6 months after the last dose of entinostat in combination with pembrolizumab (MK-3475) or 6 months after they are removed for the presence of any toxicity (early or late).

During maintenance: Patients whose primary oncologist is at one of the study sites will be followed and seen by a member of the study team at least monthly in person or by phone when study visits are not required. For patients who are followed by an oncologist outside of one of the study sites, a study team member will evaluate the patients at least monthly in person or by phone.

During 6 months post last dose or after removal from study: all patients will be evaluated by the study team at least monthly. Evaluations may be done during routine clinic visits in patients followed longitudinally at the study Cancer Center or via phone if in person visits are not possible due to logistical reasons. The study team will note the follow-up in the medical records and source documents will be sought for any change in condition related to the study or study drug.

Patients removed from study for unacceptable adverse event(s) will be followed in person or by phone until resolution or stabilization of the adverse event OR for at least 6 months after removal from study. Prior data have showed a median OS of 5 months for patients with HR-MDS who

failed 5-AZA or Decitabine. Therefore, we expect to capture most events of progression, relapse or death during the maintenance and follow-up phases of the study. For patients who are still alive at end of follow-up period, we will check social security Death Index every 3 months for 2 more years to obtain death dates for OS calculations

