Assessment of response will occur after 4 combination cycles and similar to part 1, those who achieve an objective response or SD will continue to receive the therapy till progression. Patients who progress or respond and subsequently lose response will be withdrawn from study. BM biopsy/aspirate and PB samples will be done at baseline, after first cycle of ENT monotherapy, every 2 cycles of combined therapy, and at time of progression or study discontinuation. Formal safety assessment will be performed after the first 6 patients are enrolled and each have received at least 5 cycles (i.e. 1 ENT monotherapy cycle and 4 cycles of combined therapy (DL1, DL2) for each patient) to assess for any unexpected autoimmune or other toxicity.

Primary Endpoint(s): MTD will be defined by the occurrence of DLT among 2 dose schedules (see section 5.2)

Definitions of DLT: see section 5.2

The following early stopping rule for excess toxicity in the expansion cohort will be used: We will cease enrollment in the expansion phase at the dose determined from dose escalation part of the study if we observe two or more DLTs among the first six evaluable patients enrolled in the expansion cohort. An evaluable patient is any patient who received a study drug. If the true toxicity rate is 50% or greater at the MTD then this rule will stop the trial with probability at least .89. Similarly, if the true toxicity rate is 33% at the MTD then this stopping rule will end the trial with probability .65. In that event, a new expansion cohort will

start at the dose level immediately below the dose level that was expanded. If the dose level being expanded is dose level -1, then the study will be terminated.

Secondary Endpoint(s): Overall response rate (CR, PR, and HI) as defined by the modified International working group 2006 (IWG-2006) criteria for CR, PR, HI ([Appendix A1](#) and [Appendix A2](#)) with at least 15% to be continued

Exploratory Endpoint(s):

- Median response duration for responders, median time of progression to AML, median overall survival (OS) and 1- and 2-year OS rate
- Assessment of the dynamic quantitative change in proportion of MDSCs in BM with combined therapy (target of reducing to <10%) and correlation with any observed clinical responses

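### The formal safety assessment is timed two incompatible ways, and the version in sections 5.1 and 13.1 can be blocked if one of six patients stops early

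*Combined protocol and SAP*

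**What the plan says.** Three Part 2 paragraphs describe a formal safety assessment, each with the stated aim of finding unexpected autoimmune or other toxicity.

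- **Synopsis, Part 2:** "Formal safety assessment will be performed at end of DLT-observing period", which it spells out as one entinostat cycle plus two combined cycles. It applies to each patient and "for each DL to assess for any unexpected autoimmune or other toxicity".
- **Sections 5.1 and 13.1, Part 2:** "Formal safety assessment will be performed after the first 6 patients are enrolled and each have received at least 5 cycles", which they spell out as one entinostat cycle plus four combined cycles.

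Neither 5.1 nor 13.1 says what happens if one of the six stops before cycle 5. They also do not say whether the six are the first on study or the first in the expansion cohort. The sentence sits under Part 2, but its mention of DL1 and DL2 points to the former.

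On expected survival, section 5.6 says "Prior data have showed a median OS of 5 months" for higher-risk MDS after azacitidine or decitabine failure. The synopsis gives a "median survival of less than 6 months" after DNMTi failure.

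**The concern.** The two versions differ in length (three cycles against five) and in unit (each dose level against the first six patients). A site, monitor or safety committee cannot tell which applies.

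The five-cycle version also makes a safety review conditional on six patients all staying on treatment, in a population where the plan expects short survival. Progressing patients are withdrawn (section 13.1), and a grade 3 immune-related event takes a patient off treatment (section 5.2). Under the synopsis, a patient may continue on one agent alone after a clearly attributed event. Such a patient may not accumulate four combined cycles either. The review is therefore least likely to be triggered when toxicity is removing patients, which is the situation it exists to examine.

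The timing matters because section 6.2.1 says immune-related events can appear months after the last dose, whereas DLTs are counted only in the first two combined cycles.

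**Working it through.** The plan states no probability for this trigger, so there is no figure to reproduce.

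**Inputs**
- Cycle length: "The cycle duration will be 21 days" (section 5.1). The DLT period ends at 3 × 21 = 63 days. Cycle 5 starts after 4 × 21 = 84 days and ends after 5 × 21 = 105 days.
- Median OS: 5 months (section 5.6), with 6 months as the limit implied by the synopsis. Twelve months is my assumption, as a favourable case.
- One month is taken as 30.44 days, so 84 days = 2.76 months and 105 days = 3.45 months.

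**Literal reading: first six enrolled, no replacement**

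With exponential survival (an assumption) and deaths as the only loss, the chance per patient is s = 0.5^(t/median), and the chance for all six is s^6.

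| Median | s, start of cycle 5 | All six start | s, end of cycle 5 | All six complete |
|---|---|---|---|---|
| 5 months | .682 | .10 | .620 | .06 |
| 6 months | .727 | .15 | .671 | .09 |
| 12 months (assumed) | .853 | .38 | .819 | .30 |

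For an even chance, s must be 0.5^(1/6) = .891. That corresponds to a median time on treatment of about 17 months (to start cycle 5) or 21 months (to complete it).

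**Lenient reading: six patients who have already completed cycle 3, earlier losses having been replaced**

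Only 84 − 63 = 21 days (start) or 105 − 63 = 42 days (end) remain at risk.
- 5-month median: .909^6 = .56 to start, .826^6 = .32 to complete.
- 6-month median: .923^6 = .62 to start, .853^6 = .38 to complete.

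**Adding progression**

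The documents give no time-on-treatment figure. At an assumed on-treatment median of 3 to 4 months, the literal reading gives .02 to .06 (start) and .01 to .03 (complete). The lenient reading gives .38 to .49 and .15 to .24.

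**Timing if the trigger is met**

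Section 13.2 expects 1 to 2 patients a month. The sixth patient then enrols about 5/2 = 2.5 to 5/1 = 5 months after the first and completes cycle 5 another 3.45 months later, so the review falls at roughly 6 to 8.5 months. If accrual is not paused, about 3.45 × 1 to 3.45 × 2, or 3 to 7, further patients enrol while the sixth completes five cycles.

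**The case against.** The strongest reply is that patient safety does not rest on this sentence, and most of that stands. A safety committee reviews data after every three escalation patients and may act on concerns short of a DLT (sections 5.1, 5.2, 13.1). The expansion rule of two or more DLTs in six has no five-cycle condition (sections 5.3, 12.1, 13.1). Stopping rule 1 in section 12.1 covers delayed grade 3/4 immune events from the escalation phase. Toxicity data are monitored in real time (section 5.3), and there are at least monthly calls (section 12.1). A reader might infer that the five-cycle look is the only protection against late autoimmune toxicity; stopping rule 1 shows that it is not, although that rule sets no scheduled review.

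A reader might also infer that the review would examine only patients who tolerated five cycles. The documents do not support that. The sentence sets when the review happens, not whose data it covers, and sections 11.1 and 13.5.1 keep all patients evaluable for toxicity from first treatment with the combination.

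It is tempting, too, to say the trigger would probably never be met, or to treat .06 or .10 as an upper bound. Both go too far. Sections 5.2 and 5.3 replace patients who do not complete the first two combined cycles, and if the six are counted after replacement the chance of all starting cycle 5 can exceed one half. The 5-month median is for higher-risk MDS, whereas section 3.1.1 admits MDS of any initial IPSS category, so survival may be longer. Against this, the text says enrolled rather than evaluable, and no replacement provision covers loss between the end of cycle 3 and cycle 5.

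Finally, a later look may be intended, given late immune events. That is a reason not to resolve the conflict by simply adopting the synopsis timing.

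**Conclusion.** The contradiction is certain: one assessment with one stated purpose has two timings that differ in length and unit. That the five-cycle trigger is fragile is an inference. It rests on exponential survival and the plan's own median OS, and its size depends on how the first six are counted and on whether receiving five cycles means starting or completing the fifth. At a 5-month median, deaths only, the chance that it is met runs from .06 (literal, completed) to .56 (after replacement, started). For a given median and reading, progression and toxicity can only lower it.

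The harm is limited to a scheduled formal look beyond the DLT window that may be delayed or never triggered. This should be corrected, but it does not leave the trial without safety oversight.

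**What to change.** Reconcile the synopsis, section 5.1 and section 13.1 to one statement of when the formal safety assessment takes place, and say which six patients are meant.

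If the later look is kept, use a trigger that cannot be blocked, either:
- when each of the first six patients has received five cycles or stopped treatment, whichever comes first; or
- at a fixed calendar time after the sixth enrolment.

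State that the review covers every patient who received any study drug, including those who stopped early. This adds something: sections 11.1 and 13.5.1 count toxicity from first treatment with the combination, so a patient lost during the entinostat run-in is not clearly included.

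The cost is wording in three places, with no new procedures, visits or patients.

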13.2 Sample Size/Accrual Rate

We expect to accrue 1-2 patients with MDS per month once the study is open.

Currently there is no therapy that has been shown to prolong survival in MDS in the post-DNMTi setting and that the expected best response in patients receiving supportive care only in post-DNMTi setting is negligible (1% or less). It is generally accepted that a $\geq 15\%$ ORR in the post-DNMTi is clinically meaningful and would be worth further evaluation in larger studies.

The total number of patients enrolled in the study will range from 21 to 27. The null hypothesis response rate of 1% (only supportive care) will be rejected if we observe 2 or more favorable responses. These criterion has significance level between .02 and .03 using a one-sided binomial test. This criterion has power between .84 and .93 for testing an alternative response rate of 15% with the combination therapy. Therefore, we will treat a total of 21 patients in the combination arm (6 in the first part of the study and 15 in the second part of the study).

DOMESTIC PLANNED ENROLLMENT REPORT						
Racial Categories	Ethnic Categories				Total	
	Not Hispanic or Latino		Hispanic or Latino			
	Female	Male	Female	Male		
American Indian/ Alaska Native	1	1	1	1	4	
Asian	1	1	0	0	2	
Native Hawaiian or Other Pacific Islander	1	0	0	0	1	
Black or African American	1	1	1	1	4	
White	4	4	1	1	10	
More Than One Race	0	0	0	0		
Total	8	7	3	3	21	

13.3 Stratification Factors

There are no planned stratifications for this protocol.

13.4 Analysis of Secondary Endpoints

Overall response rate: defined by the International working group 2006 (IWG-2006) criteria for CR, PR, HI ([Appendix A1](#) and [Appendix A2](#)). We will also record PFS and OS for the

MDS. These endpoints will be assessed after cycle 2 and 4 of induction therapy, and every 3 months during follow-up. Bone marrow biopsies will be done at baseline, after 1 cycle and then every 2 cycles, at end of study, and as clinically indicated (e.g. suspicion of progression, decreasing blood counts). We aim to obtain preliminary efficacy data of entinostat in combination with Pembrolizumab (MK-3475) in terms of CR, PR, HI as defined by IWG-2006 and PFS, OS. Rates of CR, PR and HI will be summarized separately by cohort and reported with an exact 95% confidence interval. Median PFS and OS will also be reported with a 95% confidence interval.

The quantitative change in MDSCs (% MDSCs by flow cytometry, QIF score by AQUA) during treatment with the ENT/anti-PD1 combined therapy will be estimated using mixed effects models to take into account the within-patient correlation. Likelihood ratio tests will be performed to confirm if random intercepts and slopes are necessary in the model. The fixed effect for change in MDSCs over time will be evaluated for significance. The variability in the rate of change in MDSCs across patients will also be examined. The association between the clinical outcome and a meaningful reduction in MDSCs, which will be defined after a review of the data, will be assessed with the chi-square test. The quantity of MDSCs at baseline and during treatment as continuous variables can also be compared between responding and non-responding patients using a t-test or Mann-Whitney U-Test, if more appropriate.

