- Analytic plan for secondary objectives/ Sample size justification: Currently there is no therapy that has been shown to prolong survival in MDS in the post-DNMTi setting and that the expected best response in patients receiving supportive care only in post-DNMTi setting is negligible (1% or less). It is generally accepted that a $\geq 15\%$ ORR in the post-DNMTi is clinically meaningful and would be worth further evaluation in larger studies. We therefore calculated that treating a total of 21 patients in the combination arm (6 in the first part of the study and 15 in the second part of the study) to test the difference of ORR between 1% (null hypothesis-supportive care only) and 15% (alternative hypothesis, combination therapy). The null hypothesis response rate of 1% will be rejected if we observe 2 or more favorable responses. This criterion has significance level between .02 and .03 using a one-sided binomial test. The criterion has power between .84 and .93 for testing an alternative response rate of 15%.
- The total number of patients enrolled in the study will range from 6 to 27.
- Analytic plan for exploratory objectives: The quantitative change in MDSCs (% MDSCs by

flow cytometry, QIF score by AQUA) during treatment with the ENT/anti-PD1 combined therapy will be estimated using mixed effects models to take into account the within-patient correlation. Likelihood ratio tests will be performed to confirm if random intercepts and slopes are necessary in the model. The fixed effect for change in MDSCs over time will be evaluated for significance. The variability in the rate of change in MDSCs across patients will also be examined. The association between the clinical outcome and a meaningful reduction in MDSCs, which will be defined after a review of the data, will be assessed with the chi-square test. The quantity of MDSCs at baseline and during treatment as continuous variables can also be compared between responding and non-responding patients using a t-test or Mann-Whitney U-Test, if more appropriate.

TABLE OF CONTENTS

SCHEMA	2
TABLE OF CONTENTS	10
1. OBJECTIVES	13
1.1 Primary Objectives.....	13
1.2 Secondary Objectives.....	13
1.3 Exploratory objectives	13
2. BACKGROUND	13
2.1 Myelodysplastic syndrome (MDS)	13
2.2 CTEP IND Agents.....	16
2.3 Rationale for combining anti-PD1 antibody with entinostat in MDS after DNMTi failure	21
2.4 Correlative Studies Background (full correlative proposal attached in Appendix J).....	21

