13.5 Reporting and Exclusions

- 13.5.1 Evaluation of toxicity: All patients will be evaluable for toxicity from the time of their first treatment with entinostat/ Pembrolizumab (MK-3475).
- 13.5.2 Evaluation of response: All patients included in the study will be assessed for response to treatment, even if there are major protocol treatment deviations or if they are ineligible. Each patient will be assigned one of the following categories: 1) complete response, 2) partial response, 3) stable disease, 4) progressive disease, 5) early death from malignant disease, 6) early death from toxicity, 7) early death because of other cause, or 9) unknown (not assessable, insufficient data). [Note: By arbitrary convention, category 9 usually designates the “unknown” status of any type of data in a clinical database.]

All of the patients who met the eligibility criteria (with the possible exception of those who received no study medication) should be included in the main analysis of the response rate. Patients in response categories 4-9 should be considered to have a treatment failure (disease progression). Thus, an incorrect treatment schedule or drug administration does not result in exclusion from the analysis of the response rate. Precise definitions for categories 4-9 will be protocol specific.

All conclusions should be based on all eligible patients. Sub-analyses may then be performed on the basis of a subset of patients, excluding those for whom major protocol deviations have been identified (e.g., early death due to other reasons, early discontinuation of treatment, major protocol violations, etc.). However, these sub-analyses may not serve as the basis for drawing conclusions concerning treatment

efficacy, and the reasons for excluding patients from the analysis should be clearly reported. The 95% confidence intervals should also be provided.

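### The exploratory MDSC-response test uses a cut chosen after data review, with nothing keeping it blind to response, in a chi-square with about three responders (minor)

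*Combined protocol and SAP*

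**What the plan says.** Section 13.4 models MDSC change "during treatment with the ENT/anti-PD1 combined therapy will be estimated using mixed effects models" and then relates outcome to "a meaningful reduction in MDSCs, which will be defined after a review of the data, will be assessed with the chi-square test". The synopsis has the same text under "Analytic plan for exploratory objectives: The quantitative change in MDSCs", and Appendix J repeats it for Specific Aim 1 and extends it to the arginase, ROS and suppression assays. The exploratory endpoint in Section 13.1 gives a "target of reducing to <10%) and correlation with any observed clinical responses", but 13.4 does not mention that target.

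As an option, 13.4 adds: "The quantity of MDSCs at baseline and during treatment as continuous variables can also be compared between responding and non-responding patients", by t-test or Mann-Whitney. It names no visit and gives this comparison no priority. For PD-L1, Appendix J (Specific Aim 2) uses a Pearson chi-square with a stated 5% cut. Section 13.2 says "The total number of patients enrolled in the study will range from 21 to 27" and takes 15% as the alternative response rate.

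**The concern.** Two features combine. The cut is fixed only after the data have been reviewed, and no text keeps response out of that review. The test is a large-sample approximation used where responders will number about three. This is the analysis that will report whether MDSC reduction tracks response, which is the trial's mechanistic hypothesis. If response were visible when the cut was set, the p-value would lose its stated meaning, and changing to an exact test would not by itself restore it. A smaller point concerns the run-in: Section 13.1 gives the comparison before and after Cycle 1 as its purpose, but 13.4 names no such estimate.

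**Working it through.** **Inputs.** N = 21 to 27, 15% response and the rule of at least 2 responses come from Section 13.2. No level is stated for the MDSC test, so two-sided .05 (Pearson X² ≥ 3.841, uncorrected) is assumed.

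**1. The plan's own figure.** With at least 2 responses, alpha = 1 − .99^N − N(.01)(.99^(N−1)), and power is the same expression with .15 and .85. N = 21 gives .0185 and .845; N = 27 gives .0297 and .928. These match the stated .02 to .03 and .84 to .93.

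**2. Responders.** 21 × .15 = 3.15 and 27 × .15 = 4.05. With R responders and M reducers, the expected count of responding reducers is R·M/N. For 3 of 21 at the most even split, the smallest expected count is 3 × 10/21 = 1.43. Bringing every count to 5 needs R × 10/21 ≥ 5 (or R × 13/27 ≥ 5), so R ≥ 11. At 15% response that has probability .00007 (N = 21) or .0011 (N = 27).

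**3. Fixed cut, 3 of 21 responders.** There are C(21,3) = 1330 equally likely responder sets under no association. Example with 10 reducers: if all three responders are reducers, X² = 21(3×11 − 0×7)²/(3×18×10×11) = 3.85, which rejects. If none is, X² = 21(0×8 − 3×10)²/5940 = 3.18, which does not. Size = C(10,3)/1330 = 120/1330 = .090. Fisher's smallest p there is also .090, so it can never reject.

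| Reducers | Chi-square size | Fisher size |
|---|---|---|
| 3 or 18 | 55/1330 = .041 | .041 |
| 4 or 17 | 106/1330 = .080 | .003 |
| 5 or 16 | 10/1330 = .008 | .008 |
| 6 or 15 | 20/1330 = .015 | .015 |
| 7 or 14 | 35/1330 = .026 | .026 |
| 8 or 13 | 56/1330 = .042 | .042 |
| 9 or 12 | 84/1330 = .063 | 0 |
| 10 or 11 | 120/1330 = .090 | 0 |

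The two tests agree in 10 of these 16 splits. Averaging over responders ~ Bin(N, .15) and independent reducers ~ Bin(N, q), with q = .2, .3 and .5 assumed:
- N = 21: chi-square .049, .041, .039; Fisher .014 throughout.
- N = 27: chi-square .046, .041, .039; Fisher .017 to .018.

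**4. Cut tuned to response (hypothetical).** Count the responder sets for which at least one admissible cut rejects.

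| Case | Chi-square, either direction | Chi-square, hypothesised direction | Fisher, either direction |
|---|---|---|---|
| 3 of 21, ≥5 per side | 240/1330 = .180 | 120/1330 = .090 | 112/1330 = .084 |
| 3 of 21, any cut | 589/1330 = .443 | 307/1330 = .231 | 190/1330 = .143 |
| 4 of 27, ≥5 per side | 3458/17550 = .197 | 1729/17550 = .099 | 2410/17550 = .137 |
| 4 of 27, any cut | 7989/17550 = .455 | 4238/17550 = .241 | 3451/17550 = .197 |

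The benchmark for the one-direction column is .05/2 = .025. In that direction Fisher gives 56/1330 = .042 and 95/1330 = .071 for 3 of 21.

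**5. The cut-free alternative.** The exact two-sided Mann-Whitney (no ties) has size 62/1330 = .047 with 3 of 21 and 862/17550 = .049 with 4 of 27. Its smallest p with 3 of 21 is 2/1330 = .0015. For an assumed 1.5 SD shift with 3 of 21, simulated power is about .57. At 10 reducers chi-square has about .72 (but size .090) and Fisher has 0.

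**6. Run-in.** Section 13.1 says Cycle 1 monotherapy is there to separate the entinostat effect from that of the combination. The 13.4 model is described in terms of combined therapy, with a single effect of time. Appendix J (SA 1.1) uses a similar combined-treatment label but schedules both the baseline and the post-Cycle-1 samples under it. The samples exist and a model over time exists; only the named contrast is missing.

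**The case against.** The measure is exploratory, and Appendix J gives a fair reason to defer the cut: baseline values and variability of MDSCs between and within patients are not yet known. That stands. It justifies waiting, but not leaving response in view when the cut is chosen.

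A reader might infer that the cut will be picked to fit response. The documents do not say so, and a cut set blind to response adds no inflation. The .18 and .44 describe what the text fails to prevent, and roughly half of each figure comes from results in the wrong direction.

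A reader might also infer that chi-square is anti-conservative here in general. It is not: it averages at or below .05 and often coincides with Fisher. Fisher alone is a trade-off between size and power, not the correction of an error. The fault lies at particular splits, though a trial reports only one of them.

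Two further readings go too far. One is that the target of under 10% has no identifiable assay: a proportion of marrow MDSCs points naturally to flow cytometry, since 13.4 pairs percentages with flow and scores with AQUA. The other is that the run-in samples are left out of the model: Appendix J places them under the same treatment label.

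Finally, Mann-Whitney is already in the plan, and Appendix J puts flow quantification of MDSCs first when aspirate is short. Both points are fair. But the comparison is only optional, with no visit named.

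**Conclusion.** The concern holds as a minor point about an exploratory analysis. The plan leaves the MDSC cut open to response data, does not say whether the under-10% target is that cut, and gives the outcome test to chi-square with about 3 of 21 (or 4 of 27) responders. If the cut were tuned, the chi-square false-positive rate would be .18 to .44 with 3 of 21, or .09 to .23 in the hypothesised direction. With a fixed cut the size runs from .008 to .090 across 3 to 18 reducers. These figures rest on the assumed two-sided .05 level, the 15% response rate and no true association. For PD-L1 only the choice of test is in question, because its cut is stated. The run-in item is a clarification. MTD, stopping and response-rate conclusions are unaffected.

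**What to change.** 1. Make the Mann-Whitney comparison in 13.4 (exact version) the lead association analysis, applied to change from baseline in % MDSC by flow at one named visit. First reconcile the marrow timing: the Section 10 calendar gives the end of Cycle 1 and then Cycles 3 and 5, while Section 11 gives after Cycles 2 and 4. Report missing samples by response group. Section 13.5 says "Patients in response categories 4-9 should be considered to have a treatment failure", so losses will probably fall mainly on non-responders.
2. Set any MDSC cut before response data are seen, and state whether it is the under-10% target. Otherwise label the cut and its p-value descriptive. The treatment-naive samples in Appendix J could inform the cut, although they are an imperfect guide to patients after DNMTi failure.
3. For the MDSC and PD-L1 2x2 tables, give the response rate in each group "reported with an exact 95% confidence interval", as 13.4 already does for response rates, with an exact p-value as supportive only.
4. As a clarification, name the baseline to end-of-Cycle-1 contrast in the mixed model.

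The cost is SAP wording and a few model degrees of freedom, with no new patients or samples. The downside is in item 3: Fisher is conservative and cannot reach .05 at some splits (3 of 21 responders with 9 to 12 reducers), which is why the continuous comparison should lead.
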